9.1 Description of the clinical investigation

This clinical investigation is part of the active medical device vigilance plan that Orthofix Srl, in agreement with its Certifying Body, has planned to actively collect clinical data relating to the use of Chimaera in a representative number of users and patients. The data obtained from this Clinical Investigation will be used to complement the pre-market clinical evaluation carried out on the Chimaera with post-market clinical data from the use of the device in normal clinical practice (more details reported in the rationale of the Clinical Investigation).

9.2 Design of the Clinical Investigation

The present clinical investigation is of the following type:

- Observational (as ascertained in the feasibility phase, the procedures reported in this Protocol are part of the normal clinical practice of the Centers involved);
- post-market (the medical device observed has a CE mark and is already used in the Sites involved);
- prospective (clinical data will be collected from patients who will be treated with the observed device after signing the informed consent);
- uncontrolled (only the medical device under study will be observed);
- non-randomized (since the Survey is observational and uncontrolled, a randomized assignment of the medical device is not applicable);
- multicenter (the Survey will be conducted in 8 Centers);
- national (the Sites involved are all located in Italy).

Considering the purpose and design described above, this Clinical Investigation falls within the type of studies defined as "*Post Market Clinical Follow-up (PMCF) study*" (more details in MEDDEV 2.12/2 rev. 2).

9.3 Objectives of the Clinical Investigation

The purpose of this Clinical Investigation is to actively collect clinical data related to the use of the *Chimaera* in a representative number of users and elderly patients with proximal femur fracture, observed in the short (1, 3 and 6 months) and medium (1 year) period after the application of the device.

- The primary objective of the Clinical Investigation is to evaluate the safety of the *Chimaera* which will be measured in terms of serious device-related adverse events.
- The secondary objective of the Clinical Investigation is to evaluate the clinical efficacy of the *Chimaera* through a specific functional score.

Note:

For more details regarding the measurement of primary and secondary objectives, please refer to the "*Endpoint*" paragraph of this Protocol.

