In fact, about 10% of patients over 75 years of age who suffer a hip fracture die within 30 days of surgery at cause of intra- and post-operative complications that aggravate a general state of health already compromised by pre-existing comorbidities. In addition, the drastic change in life triggered by the severe disability caused by this fracture, which often leads to a substantial loss of autonomy, causes the 1-year mortality rate to rise between 14% and 36%.⁵ 42% of survivors do not return to pre-fracture mobility, 35% are unable to walk independently, 20% are unable to shop independently, and approximately 20% enter a long-term care facility during the first year after a fracture.⁴

In an attempt to lengthen the expectations and quality of life of these patients, the most recent guidelines suggest a multidisciplinary approach for the treatment of unstable hip fractures that involves, where possible, the close collaboration of different specialists such as the orthopedist, the geriatrician, the anesthesiologist, the cardiologist and the physiatrist. Although a consensus on the best possible treatment has not yet been found, several studies demonstrate a real benefit in the use of multidisciplinary protocols that always provide for timely surgical treatment of the fracture.^{5,6}

To date, there are several treatment options available for unstable hip fractures, each with advantages and disadvantages, including external fixation systems, internal fixation systems and partial or total hip replacement. In the field of internal fixation, the use of intramedullary nails has become increasingly popular due to the biomechanical advantages they provide in many indications compared to other synthetic media such as plates or dynamic cephalic screws.

However, the percentage of complications considered serious, i.e. requiring reoperation, associated with intramedullary nail treatment, such as cut-out, lateral protrusion of the cephalic screw and peri-implantation fractures, remains clinically significant (overall they can affect up to 30% of patients treated).

The *Chimaera* developed by Orthofix Srl is an intramedullary nail also indicated for the treatment of proximal femur fractures that integrates technical features specifically designed to decrease the probability of encountering the most serious and frequent complications in this type of treatment.

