9.4 Endpoint

In the present Clinical Investigation, the two variables chosen as *the primary and secondary endpoints* to measure the primary and secondary objectives of the Survey also coincide with the measures of response to treatment, in particular:

- Primary endpoint (security measure):

the safety of the *Chimaera* will be measured by the percentage of patients who within a 6-month observation period, due to serious adverse events related to *the Chimaera*, will have to undergo a second operation to continue with the treatment of the proximal femur fracture.

- Secondary endpoint (efficacy measure):

the effectiveness of the treatment carried out with *Chimaera* will be measured through the Bowers & Parker functional score for the evaluation of the patient's functional recovery.

Note:

Bowers & Parker's functional score⁷ It is a validated and unanimously recognized reliable score for the evaluation of patients treated following a hip fracture. This score assesses the patient's functional recovery (in terms of pain, walking ability and social independence) compared to the patient's condition before the fracture. The Bowers & Parker score also has predictive value for assessing the long-term mortality of the treated patient, and for planning short-term rehabilitation activities.

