9.5 Variables to measure

The primary endpoint (safety measure) of the present Clinical Investigation will be measured as follows:

- the correlation of the serious adverse event to the *Chimaera* will be freely assigned by the Investigator according to the following options: unrelated/potentially related/certainly related. Serious events potentially or certainly related to the *Chimaera* will be included in the calculation of the security measure.
- It is understood that, for serious events judged to be potentially or certainly related to the *Chimaera*, the Sponsor reserves the right to supplement the Investigator's assessment with an opinion from an independent orthopaedic physician and with a technical analysis of the implanted and removed device to proceed with the second intervention. Following these analyses, if the removed device complies with the design specifications, and if the independent orthopedist finds an operating technique error in the primary implant, in agreement with the Investigator, the event initially classified as potentially or certainly related to the *Chimaera* may be reclassified as unrelated and, therefore, will be excluded from the calculation of the safety measure. Similarly, serious adverse events due to use that does not comply with the manufacturer's instructions for use, otherwise referred to as *off label use*, will be excluded from the calculation of the safety measure.

The *secondary endpoint* (efficacy measure) of the present Clinical Investigation will be measured as follows:

- The Investigator will fill out a scale (Appendix 1) for each patient at each of the follow-up visits (1, 3, 6, and 12 months). If necessary, a translation of the scale into Italian is also provided to support comprehension.
- As suggested by the authors, the scale can be filled in by the Investigator on the basis of the answers provided by the patient, even by telephone. Given the type of patients that will be recruited, mostly non-self-sufficient elderly people who cannot always be moved easily, this procedure will not involve additional risks for the patient and should limit the number of patients that cannot be assessed due to lack of data on the secondary *endpoint*.

Data for the primary and secondary *endpoints* will be:

- reported in the patient's medical record and recorded in the electronic database provided free of charge by the Sponsor to each Investigator to collect the data of the Clinical Investigation;

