9.11 Medical-Surgical Procedures and Follow-up of the Clinical Investigation

After obtaining informed consent, the physician will include in the study those patients who, at the screening visit (Visit 0), meet all selection criteria. During the screening visit, the Investigator will also collect demographic data and the patient's medical history.

Enrolled patients, as would also occur if they chose not to participate in the present Investigation, will undergo the surgical procedure (Visit 1) required for the application of the investigational medical device (Chimaera), which marks the beginning of the treatment period.

Following the surgery, the patient will attend five subsequent visits. The first three visits after the surgical procedure are part of the treatment period and are:

- the visit performed at hospital discharge (Visit 2), which, unless complications occur, will take place within 10 days after the date of surgery. During this visit, the physician will perform routine assessments to confirm that the operation and postoperative course have proceeded appropriately;
- the following two visits (Visits 3 and 4), were conducted at 1 month and 3 months after the date of surgery, respectively. These visits conclude the treatment period which, in the absence of complications, is expected to be within 8–12 weeks from the date of surgery, with the consolidation of the treated proximal femoral fracture. Healing will be assessed by the Investigator through radiographic evaluation, performing a qualitative assessment of bone density at the fracture site and the alignment of the bone fragments. Starting from Visit 4 and at all subsequent visits, the Investigator will also complete the Bowers & Parker functional score (efficacy measure) to assess the patient's functional recovery.

For these patients, device removal is not planned unless required due to serious adverse events necessitating a second surgical procedure to complete the treatment of the fracture (safety measure). Once the treatment period is concluded, the follow-up period begins, during which two visits will be conducted (Visits 5 and 6), respectively at 6 months and 1 year after the date of surgery. During these visits, clinical data will be collected to monitor the progression of fracture consolidation, the patient's functional recovery, and the occurrence of any medium-term adverse events.

[figure not shown]

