Foreseeable adverse events from the use of *Chimaera*, as identified by the risk analysis carried out on the product at the design stage, are described in the "POSSIBLE SIDE EFFECTS" section of the package insert of the device (http://abs.orthofix.it/db/resources/PQ_HFN.pdf) in the section.

This clinical investigation is observational and therefore does not involve additional risks for patients and investigators.

Definitions:

- An AE is any unwanted experience associated with the use of the device in a patient.
- An AE is described as a serious AE when the patient, due to that AE:
 - dies;
 - suffers a potentially fatal event;
 - undergoes a prolongation of hospitalization;
 - he undergoes a second hospitalization;
 - reports a permanent disability
 - Reports a birth defect.

Adverse events and effects that will occur during the study will be classified and reported to the Sponsor through the appropriate form provided with the study documentation. The Investigator will be obliged to notify the Sponsor of a serious adverse event within 24 hours of becoming aware of it.

In compliance with the reference legislation (art. 9 of Legislative Decree 46/97 and MEDDEV 2.12.1) moreover, through the use of the ministerial forms, the Investigator and the Sponsor will report to the Ministry of Health all accidents that will occur during the use of the medical device subject to this study by means of a specific report to office V of the DGDMF, as well as to the local EC.

18 Statistics

For this clinical investigation, there are no statistical hypotheses to be tested or direct comparisons with other devices clinically equivalent to the *Chimaera*, so no threshold has been defined to be considered safe and effective.

However, for the sole purpose of recruiting enough patients to be able to consider the data collected for the *primary endpoint* (safety measure of response to treatment) reliable compared to the data reported in the literature, a sample sizing calculation was still performed.

For Chimaera-equivalent devices, the proportion of patients who underwent a second surgery (due to serious device-related adverse events and/or due to device failure) in the literature is reported to be between 3% and 10% depending on the study considered. A sample size calculation was then performed in order to limit the upper limit of the 95% confidence interval of the proportion of patients with second surgery to below 10%.

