The following table shows the number of patients and the upper limit of the confidence interval for different possible values of the percentage of the primary *endpoint* (calculations were made using the statistical method of the exact binomial):

Percentage of patients with second intervention	Upper limit of the 95% confidence interval	Number of patients observed
3%	8.518%	100
4%	9.926%	100
5%	9.614%	160
6%	9.703%	250
7%	9.958%	400

Based on the frequencies of serious device-related adverse events and/or device failures received by Orthofix Srl through the passive medical device vigilance system since the device was placed on the market, the expected percentage for the primary *endpoint* is no more than 6%. Therefore, the expected enrollment of 400 patients that will potentially allow us to obtain a sample of 300 evaluable patients is considered adequate for the type and objectives of the present clinical investigation.

The clinical data collected during this Clinical Survey will be analyzed through descriptive statistics:

- the *primary endpoint* will be presented as a percentage value and the corresponding 95% confidence interval;
- the *secondary endpoint* (Bowers & Parker functional score) and other radiographic parameters will be presented via quantitative descriptive statistics (mean, standard deviation, median, minimum, maximum, 95% confidence interval).

During the present Clinical Investigation, if necessary, an interim statistical analysis of the collected data could be carried out, e.g. when all patients have completed the third post-operative check-up (expected within 6 months from the date of operation).

The clinical data obtained from this Clinical Investigation will be used to complete the evaluation of the clinical performance and safety of the *Chimaera* in order to confirm that the device can be considered

effective and safe as assumed under development based on pre-clinical evaluations carried out for obtaining the CE mark.

19 Dissemination of results

The Investigators and the Sponsor undertake to keep the clinical data collected through this Clinical Investigation confidential and confidential until the information is made public in anonymized form by the Sponsor at the end of the Investigation.

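### The primary objective covers all serious device-related adverse events, but the endpoint in 9.4 counts only those leading to a second operation, and the sections disagree on what is counted

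*Combined protocol and SAP*

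**What the plan says.** Section 9.3 states that safety will be "measured in terms of serious device-related adverse events" and refers the reader to the endpoint section for details. Section 9.4 defines the measure as the "percentage of patients who within a 6-month observation period", because of serious adverse events related to the device, "will have to undergo a second operation to continue with the treatment of the proximal femur fracture". Section 9.11 repeats the condition, speaking of "serious adverse events necessitating a second surgical procedure to complete the treatment of the fracture (safety measure" in parentheses. The sizing in section 18 is likewise about patients with a second surgery.

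Section 9.5, which sets out how the primary endpoint is measured, reads differently. Serious events graded potentially or certainly related "will be included in the calculation of the security measure", and that sentence does not mention re-operation.

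The word serious also has two meanings. The background (section 2) speaks of "complications considered serious, i.e. requiring reoperation". Section 17 gives a wider list, covering death, a potentially fatal event, a second hospitalization, permanent disability, and the case where the patient "undergoes a prolongation of hospitalization".

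For the analysis, section 18 says that the primary endpoint "will be presented as a percentage value and the corresponding 95% confidence interval". It names no summary of all serious device-related events.

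**The concern.** The endpoint adds a condition that the objective does not have. A patient with a device-related event that is serious under section 17, but who has no second operation, falls within the objective and outside the 9.4 numerator. No section says how to classify that patient, or one who dies before a re-operation could take place.

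Two things are at stake. First, an analyst working from 9.4 and one working from 9.5 could report different primary results from the same data. Second, section 18 says the data will be used to confirm that the device is effective and safe. If only the narrower figure is reported, the stated primary objective has no figure of its own.

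**Working it through.** **1. The plan's own figures.** The table in section 18 uses exact binomial limits. With x events in n patients, the two-sided 95% upper limit is the 0.975 quantile of a Beta(x + 1, n − x) distribution. For x/n = 3/100, 4/100, 8/160, 15/250 and 28/400 this gives 8.518%, 9.926%, 9.614%, 9.703% and 9.958%, matching all five rows. Enrolment also reproduces: 300 / (1 − 0.25) = 400. There is no arithmetic error; the question is what is counted.

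**2. What each section counts.**

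| Section | Counted | Second operation required? |
|---|---|---|
| 9.3 | serious device-related events | not stated; refers to 9.4 |
| 9.4 | patients, within 6 months | yes |
| 9.5 | serious events, potentially or certainly related | not stated |
| 9.11 | serious events that make a second procedure necessary | yes |
| 18, sizing | patients with second surgery | yes |
| 18, basis of the expected 6% | vigilance reports of serious device-related events and of device failures | no |

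The planning inputs therefore mix two quantities. The literature range of 3% to 10% is for second surgery, while the expected rate of at most 6% comes from the broader class.

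**3. Direction.** Let B be the number of patients with any serious device-related event and A the number of those who also meet the second-operation condition. With the same relatedness rules, time window and denominator N, A is a subset of B, so A/N ≤ B/N. The 9.4 rate can equal the rate the objective names or lie below it, but cannot exceed it.

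**4. Size, as illustration only.** The documents do not give the share of serious device-related events that are not re-operated, so B − A cannot be calculated. What can be shown is how far one or two events move the result at the planned 300 evaluable patients:

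- 18/300 = 6.00%, upper limit 9.32%
- 19/300 = 6.33%, upper limit 9.71%
- 20/300 = 6.67%, upper limit 10.11%

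Each added event raises the rate by 1/300 = 0.33 percentage points. Two raise the upper limit by 10.11 − 9.32 = 0.79 points.

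**5. Data available.** The table in 9.13 schedules safety measures at Visits 1 to 6, 9.5 has the Investigator grade relatedness, and section 10 plans full monitoring of adverse event information. The broader count needs no new visit.

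**The case against.** The strongest defence is that 9.3 does not stand alone: its note points to 9.4, which makes the objective operational. On the background's usage, where serious means requiring re-operation, objective and endpoint coincide. Section 9.5 can be read as settling only which relatedness grades qualify, since it goes on to discuss analysis of a device removed for a second intervention. Re-operation is also the measure in the literature used for sizing. The last point stands and is a good reason to keep the endpoint. The rest does not remove the conflict, because section 17 is the protocol's formal definition of serious and is wider, and 9.5 does not state the restriction.

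The wording of 9.4 and 9.11 could also mean that surgery is needed rather than performed, which would capture a patient judged to need an operation that never took place. Section 18 describes the literature rate as patients who underwent a second surgery. The point is unsettled, and this is a further reason to clarify it.

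A reader might infer more than the documents support:

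- *That patients too frail for re-operation count as successes.* The plan defines no success category, and section 18 disclaims any threshold. The accurate statement is that their event is not counted under 9.4.
- *That such patients remain in the denominator as event-free.* The denominator is not stated. Patients who stop before Visit 4, including by death, are called non-assessable and may be replaced (9.14 to 9.16), although their data are still to be analysed.
- *That frail patients are known to go without re-operation.* The protocol describes an elderly, mostly non-self-sufficient population with one-year mortality of up to 36%, so this is plausible, but it is nowhere stated or quantified.
- *That a true rate can be found by inflating 6%.* Assuming 10% to 30% not re-operated gives 6/0.9 = 6.7% to 6/0.7 = 8.6%. The share is a pure assumption, and the 6% already rests on the broader class of events, so the inflation may count the same events twice.

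**Conclusion.** The concern holds in a limited form. Under the section 17 definition, the endpoint in 9.4, 9.11 and the section 18 sizing is narrower than the objective in 9.3, and 9.5 does not carry the same restriction. Following 9.4 leaves serious device-related events without re-operation out of the primary figure. The direction of the difference is certain on a common denominator, window and relatedness rule; its size cannot be derived from the documents. The limits of 9.32%, 9.71% and 10.11% for 18, 19 and 20 events among 300 show sensitivity to small counts and are not an estimate of bias.

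A reader might take the step past 10% at 20 events as a failed safety criterion. It is not one. The 10% is a precision target for second surgery, so a rate of all serious device-related events should not be compared with it. The re-operation endpoint is usable for its comparison; what is missing is one consistent definition and a summary that answers the stated objective.

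**What to change.** 1. Keep the re-operation endpoint for comparison with the second-surgery literature.
2. Reconcile 9.3, 9.4, 9.5, 9.11, 17 and 18 on what is counted. Say which meaning of serious applies, whether the operation must be performed or only needed, and how an event without re-operation and a death before re-operation are classified.
3. State the denominator of the primary percentage, for example all implanted patients.
4. In section 18, add the proportion of patients with any serious event potentially or certainly related to the device, re-operated or not, with an exact 95% interval at Months 6 and 12. Use the same 9.5 relatedness rules and the same denominator as the primary figure. Beside it, give the number not re-operated, including deaths before re-operation.
5. State that this broader rate is not to be compared with the 10% sizing target.

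The cost is a protocol clarification and a few descriptive rows from safety data already scheduled for collection. Sample size and visits do not change. The downside for the sponsor is a less favourable safety figure beside the primary one.
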